4.0 HEALTHY HUMAN SUBJECTS

Minority Inclusion and Non-Discriminatory Statement: Subjects will be recruited from the general population of western Pennsylvania and West Virginia regions. No exclusion criteria will be established based on race, ethnicity, or gender. Subjects will be at least 18 years of age and less than age 55, and no prisoners will be used for this study. The upper age range of 55 was imposed due to the intensive exercise components of this study. Both men and women will be included in the study; however, subjects for either gender should not exceed 68% of total evaluable subjects to better demonstrate US workforce representation (i.e. no more than 17 evaluable subjects should be used from one gender)

4.1 Inclusion Criteria

- Ability to understand, the willingness to participate, and the completion of a written informed consent document
- Understands spoken and written English language as required for consent and instruction
- Age > 18 years old and < 55 years old
- OSHA/NPPTL Medical Evaluation Form completed by the participant and reviewed/signed by a U.S. licensed health professional such as a registered nurse or certified registered nurse practitioner (Appendix D.)
- If a subject reports "yes" to any medical condition listed on the OSHA/NPPTL Medical Evaluation Form (Appendix D.) in Part B for Questions 2, or 10 to 15, a Certified Registered Nurse Practitioner/Registered Nurse must review the subject's current and past medical history and provide written documented clearance for the subject to participate.

- NPPTL Screening Medical Review completed by participant and U.S. licensed health professional (Appendix E.)
 - Two head and face measurements using a tape measure and calipers, values recorded on the anthropometric data form (Appendix J)
 - NIOSH/NPPTL Bivariate Panel (Fig. 2 and Table 2) facial measurements and cell category availability based on their allocation to provide representation of the US workforce (if a cell category is full the subject will be considered a screen fail, however can rescreen at a later date if a subject in their cell category is not considered evaluable).
 - Subject will pass fit testing for three models of tight fitting PAPRs, with sizes provided by the NIOSH/NPPTL Bivariate Panel
 - Subject completion of the Subject Data Form (Appendix F), including agreement to refrain from caffeine consumption 12 hours prior to and during testing and smoking 1 hour prior to and during testing
 - Complete maximal graded exercise testing with treadmill protocol (Appendix K) and achieve a maximal oxygen consumption **above** "Poor" category (e.g. Fair to Excellent categories required for inclusion) based on American College of Sports Medicine Fitness Categories for Maximal Aerobic Power (treadmill test)
 - Review of the NPPTL General Photo Release Form (Appendix U).

4.2 Exclusion Criteria

- Facial hair, jewelry, or head and neck injury which may interfere with wearing a PAPR
- Chronic or current pulmonary or lung problems reported by subject (reports "yes" to any item in Part B. questions 3 or 4) on OSHA/NPPTL Medical Evaluation Form (Appendix D.) These are absolute exclusions.
- Self-reported chronic or current cardiovascular problems (reports "yes" to any item in Part B. questions 5 or 6) on OSHA/NPPTL Medical Evaluation Form (Appendix D.). These are absolute exclusions.
- Self-reported medications for chronic problems (reports "yes" to any item in Part B. question 7) on OSHA/NPPTL Medical Evaluation Form (Appendix D.) This is a relative exclusion and will be reviewed by a medical monitor CRNP to determine if it is contraindicated with the tests for the study. Documentation of review and rationale will be completed by the medical monitor CRNP.
- Prior problems using a respirator as reported in Part B. question 8 of the OSHA/NPPTL Medical Evaluation Form (Appendix D.). This is a relative exclusion, and must be reviewed by medical monitor certified registered nurse practitioner and PI on a case by case basis. If it is determined to not affect risk for the study interventions in this trial, consideration for subject participation may be permissible and should be documented with rationale on why it is not applicable to this study as an exclusion.
- Pregnancy. All female subjects of child-bearing potential will be required to complete a
 urine pregnancy test provided by NPPTL prior to enrollment in the study and again prior
 to each study visit, not to exceed more than once every seven days, at the first visit of that
 week. A U.S. licensed health professional will interpret the pregnancy test and approve or
 deny participation based on results. A woman is considered non-child bearing if she
 reports menopause or surgical sterilization, and therefore would not require pregnancy
 testing.
- Experiencing any clinically contraindicated signs or symptoms during the maximal graded exercise testing with a treadmill protocol, such as abnormalities deemed to be a

614 615

616 617 618

619 620

621

622 623 624

625

626

627 628 629

631 632 633

634

630

635 636 637

> 638 639 640

641

642 643 644

645

646

647 648 649

650 651 652

653 654 655

656 657

658

risk during the continuous EKG.

- Self-reported diabetes or chronic kidney disease (reports "yes" to question 2b in Part B of Appendix D.). This is an absolute exclusion.
- Self-reported nutritional supplements, reported on NPPTL Medical Screening Evaluation (Appendix E). This is a relative exclusion and will be reviewed by a medical monitor CRNP to determine if it is contraindicated with the tests for the study. Documentation of review and rationale will be completed by the medical monitor CRNP.

5.0 PROCEDURES AND EVALUATIONS

5.1 **Screening**

- 1) Subjects will be identified by volunteerism using a Recruitment Flyer (Appendix B) which will be placed in local public places.
- 2) Study staff will review the Informed Consent Form (Appendix C) with each subject explaining all risks and benefits as well as subject responsibilities for participation. All questions will be answered for subjects. If a subject decides to participate, they must sign and date the consent form and a delegated study staff member must sign and date the consent form thereafter. A copy must be provided to the subject upon completion,
- 3) Once a subject is consented, they will first undergo two facial measurements used to place the subject into a NIOSH/NPPTL Bivariate Panel cell category. If the cell category is full, based on a first come first serve basis, the subject will be screen failed, and informed they will be contacted for re-screen in the event an opening occurs later on in their cell category.
- 4) Subjects will next complete the OSHA/NPPTL Medical Evaluation form (Appendix D), the NPPTL Screening Medical Review (Appendix E), the Subject Data Form (Appendix F), and the NPPTL General Photo Release (Appendix U). The medical questionnaires and evaluations will be reviewed by a U.S. licensed health professional at NPPTL to determine eligibility for safety.

Urine Pregnancy Test

- A U.S. licensed health professional will inform female subjects of childbearing potential the instructions on how to complete the urine pregnancy test in a private setting. A private bathroom will be provided to the subject during the test and the U.S. licensed health professional will wait outside of the restroom to read the result.
- If the result is positive, the U.S. licensed health professional will provide the subject with a private area to talk, and instruct the participant that they should consult with their primary care provider for follow up confirmation and education. They will also be informed they will be excluded from the study at this time, as per the consent.
- If negative, the participant will be able to continue screening
- Whether positive or negative the result will be added to the Point of Care Testing data capture form (Appendix G) and a same-day copy will be provided to the subject if they would like a copy, with instruction to provide it to their primary care provider.
- 5) If safe to proceed after medical evaluations and based on NIOSH/NPPTL bivariate panel cell category, subjects will next complete quantitative fit testing for two tight-fitting

- 659
- 660 661
- 663
- 667
- 670

- 677

- 681

- 688

703

- 662
- 664
- 665 666
- 668 669
- 671 672
- 673 674 675
- 676
- 678 679
- 680
- 682 683
- 684 685
- 686 687
- 689 690 691
- 692 693 694
- 695 696 697
- 698 699
- 701 702
- 704 705
- 706

- PAPR models to confirm bivariate panel allocation.
- 6) Lastly, if eligible based on all above screening requirements, subjects will undergo a Maximal Graded Exercise Test (Appendix K) according to the Bruce protocol (Wasserman, 2012) to provide individual subject safety parameters and additional medical evaluations.
- 7) Finally, if eligibility for registration is confirmed by the study team, the subject will be registered and scheduled for their study visits. If a subject screen fails for any reason, their data will be kept and a study team member will inform them of their exclusion. If a subject screen fails due to their cell category in the bivariate panel being full, they will be informed that they may be called back for participation and in the event a subject in their cell category becomes unevaluable during the study.

5.2 **Work Rate Determination Test Procedures**

- 1) Subjects will be equipped with a silicone-rubber oronasal facemask connected to a metabolic cart, which will measure expired air for CO₂ and O₂, and minute ventilation (V_e). They will also be equipped with a heart rate monitor.
- 2) Test subjects will be instructed on how to communicate with the test operator whenever they feel unable to continue. The tests will be terminated immediately if a subject or investigator notes any potential adverse events or safety parameters reached.
- 3) After connecting the subjects to the metabolic cart, the subject will perform the 10exercise regime shown in Table 3.
- 4) After completing the regime, the subjects will be disconnected from the metabolic cart.

5.3 **SWPF Test Procedures**

- 1) Subjects will wear a Tyvek suit or lab coat and foot protection, based on subject preference, to cover their personal clothes and shoes during testing.
- 2) PAPR batteries will be tested by study staff to make sure they are fully charged per the manufacturer's instructions. Batteries will be charged for at least 12 hours prior to use.
- 3) A test operator will: a) turning the blower on, b) adjust/verify the PAPR flow rate, and c) assist the subject with donning each PAPR model using the manufacturer's directions.
- 4) During Phase II only, the PAPR flow rate first to be tested will be the fixed manufacture
- 5) A fingertip-pulse oximeter will be worn by each subject in order to obtain oxygen saturation information. When wearing the PAPR, the test subjects will be instructed on how to communicate with the test operator whenever they feel unable to continue. The tests will be terminated immediately if a subject or investigator notes any potential adverse events or safety parameters reached (Section 7)
- 6) Once the corn oil aerosol concentration in the chamber reaches approximately 20-40 mg/m, the subject will enter the chamber wearing the PAPR model assigned with the blower running. The test operator will connect: 1) a pressure line and 2) all sample lines to particle detector systems. Dustrak and Laser photometer will be used to measure simultaneously to measure the upstream (outside the PAPR) and downstream (inside the PAPR) test aerosol (Fig. 4A & Fig. 4B).
 - 7) After connecting all sample lines, the subject will perform either the 10-exercise regimen shown in Table 3 (Section 3.3), or one of the three 2-exercise regimes in Table 6 (Section 3.4) dependent on the Phase they are enrolled into. Data from the Dustrak and Laser photometer will be recorded and each individual exercise SWPF will be calculated as a ratio of the upstream and downstream particle concentrations.

8) After completing testing with a PAPR and specified flow rate, the subject will exit the test chamber and remove the PAPR. Subjects resting vital signs must return to near baseline and a minimum of a ten-minute break must be provided to the subject between each exercise regimen test if multiple scheduled in one day.

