3.3 Phase II

the GXT.

Phase II is designed to test flow rate effects on individual exercises & regimen overall SWPF values. This phase will include the 25 evaluable subjects from Phase I if they are interested in continued participation. If subjects from Phase I decline or are no longer eligible, additional subjects may be consented and screened for recruitment utilizing the modified screening requirements from Phase I (Appendix A, Study Calendar 1). Phase II will use the exercise regimen (Table 3.) and work rates determined in Phase I, with eight different PAPR models and two flow rates for each PAPR. Subject's will complete one 30-minute regimen = ten, 3 minute exercises completed in sequential order from light to hard work rates with breaks following the hard exercises (see Section 3.2) for sequence. 25 subjects x 8 PAPR models x 2 flow rates x 2 regimen replicates = 800 overall SWPF values (based on 10 exercises). Three Way Repeated Measures ANOVA will be used to analyze the data.

Each subject will come in to test 2 PAPRs and 2 flow rates per visit for approximately 3 hours, 392 for a total of 4 visits (~12 total hours) to complete the first replicate of tests. The subjects will 393 repeat the same procedure for the second replicate, meaning each subject will complete Phase II 394 over the course of 8 visits of approximately 3 hours per visit (~24 total hours). It is estimated that this phase will take 6 to 9 months (November 2019-July 2020). 396

PAPR Models

391

395

397

398

399

400

401

402

403

404

405 406

407

408 409

410

Eight PAPR models (4 PAPRs with loose-fitting hoods, 2 loose-fitting facepiece PAPRs with helmets, and 2 tight-fitting PAPRs) were selected for this study (Table 5.). The models were selected based on: 1) prevalence of respirators in healthcare (Wizner, 2016) and 2) their commercial availability. The assigned protection factors for each PAPR is 25 or 1000. Tight fitting full facepieces (models 1-2) have a tight seal along the chin and sides of face. Loosefitting full hoods (models 3-6) have a shroud covering the shoulders down to the mid-torso. Loose-fitting facepieces (models 7-8) have a cuff that loosely contacts the chin and the sides of the face. Each PAPR device weight will be measured and recorded. All PAPR devices used in this study will be set at the same airflow rate. Each subject will be asked to complete the comfort survey after each PAPR tested with all three flow rates in Phase II (Appendix M).

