Table 5. Phase II PAPR Models

#	PAPR MODEL	OSHA APF	RIC DESIGN
			tight-fitting full
1	Bullard EVA	1000	facepiece
	2504.00	1000	tight-fitting full
2	MSA OptimAir	1000	facepiece
3	3M Versaflo		
	hood (S-403L (M/L size)	1000	loose-fitting full hood
	hood (S-403S (S/M size)	1000	
4	ILC Dover Sentinel XL		
	S-2019-10 (one-size)	1000	loose-fitting full hood
5	Bullard EVA		
	20TIC hood (one-size)	1000	loose-fitting full hood
6	Maxair Helmet CAPR w/ HE filter (Bio-Medical Devices, Inc.)		
	2261-01ML	25	loose-fitting full hood
	2261-01SM	25	
7	Maxair Helmet CAPR w/ HE filter (Bio-Medical Devices, Inc.)	25	loose-fitting facepiece

[figure not shown]

	3M VersaFlow w/ S133 cuff		
8	facepiece	25	loose-fitting facepiece

Flow Rates

 The two PAPR airflow rates tested in Phase II include: 1) 170 L/min for loose-fitting PAPRs and 115 L/min for tight-fitting PAPRs (based on the current NIOSH minimum certification airflow rates) and 2) 125 L/min for loose-fitting PAPRs and 100 L/min for tight-fitting PAPRs (experimental airflow rates below the NIOSH certification requirement). Flow rates at and below the NIOSH certification minimum, PAPRs will be modified and therefore not NIOSH certified. Modifications to these devices will reduce airflow by one of two ways as determined by the study team: 1) controlling voltage to the PAPR motor, 2) installing a 3-way valve into the blower hose (if equipped) to bleed-off excess flow (Figure 3).

Figure 3. Subject Wearing a PAPR with Fixed Airflow Valve

Simulated Workplace Protection Factor

SWPF testing will take place in both Phase II and Phase III, following the work rate determination in Phase I. Test subjects wearing PAPR will enter the test chamber and complete the exercise regimen (Table 3.) against a corn oil challenge aerosol.

For this test, a TSI Rear Light Scattering Laser Photometer, model 8587A, will be used to measure aerosol concentration inside of the respirators. A TSI model 8520, Dustrak Aerosol Monitor will be used to monitor chamber particle concentrations. Data collected by the laser photometer will be recorded on the NIOSH Dynamic Fit Software. Data will be analyzed using a three-way repeated measures ANOVA with subject number, model, and work rate, and the log transformed SWPF of each test as the dependent variable. The relative importance of each variable to PAPR performance will be determined. The SWPF will be calculated in two steps as follows:

1. Ratio of the Upstream and Downstream Particle Concentrations

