⁶Replicates 1, 2, & 3 each include one 30-minute exercise regimen completed by the subject while monitored with a metabolic cart.

⁷Prior to each study visits exercise regimen test, subjects and a U.S. licensed health professional must complete the NPPTL Pre Visit Medical Evaluation form (Appendix L)

⁸After the subject completes the exercise regimen, they must be given a minimum of a ten-minute break before post visit medical evaluation (Appendix O) and a U.S. licensed health professional must review their pre and post test medical evaluations (Appendices M. & P) and approve discharge before they are dismissed from the visit.

After 25 evaluable subjects complete replicate 1 study interventions, an interim data analysis will be completed. If additional attempts for all subjects are found to be warranted for (replicate 2 and/or 3), subjects may return and complete replicate 2 and replicate 3 during the same visit. If this occurs then subjects must be given a minimum of a ten-minute break in between attempts, and their vital signs must be assessed and returned to baseline values prior to initiating third attempt.

¹⁰Documentation of General Photo release agreement or decline must be recorded for each subject (Appendix U)

2. Phase II Study Calendar 1492

Visit #1 ^{1,4} (3 hours)	Visit #2 ⁴ (3 hours)	Visit #3 ⁴ (3 hours)
Pregnancy Test ²	Pregnancy Test ²	Pregnancy Test ²
NPPTL Pre Visit Medical Evaluation ³	NPPTL Pre Visit Medical Evaluation ³	NPPTL Pre Visit Medical Evaluation ³
Model 1: Flow Rate 1 & 2 Exercise Regimen (Table 3): Replicate 1	Model 3: Flow Rate 1 & 2 Exercise Regimen (Table 3): Replicate 1	Model 5: Flow Rate 1 & 2 Exercise Regimen (Table 3): Replicate 1
Phase II Survey	Phase II Survey	Phase II Survey
Model 2: Flow Rate 1 & 2 Exercise Regimen (Table 3): Replicate 1	Model 4: Flow Rate 1 & 2 Exercise Regimen (Table 3): Replicate 1	Model 6: Flow Rate 1 & 2 Exercise Regimen (Table 3): Replicate 1
Phase II Survey	Phase II Survey	Phase II Survey
NPPTL Post Visit Medical Evaluation ⁵	NPPTL Post Visit Medical Evaluation ⁵	NPPTL Post Visit Medical Evaluation ⁵

Visit #4 ⁴ (3 hours)	Visit #5 ⁶ (3 hours)	Visit #6 ⁶ (3 hours)
Pregnancy Test ²	Pregnancy Test ²	Pregnancy Test ²
NPPTL Pre Visit Medical Evaluation ³	NPPTL Pre Visit Medical Evaluation ³	NPPTL Pre Visit Medical Evaluation ³

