Model 7: Flow Rate 1 & 2 Exercise Regimen (Table 3): Replicate 1	Model 1: Flow Rate 1 & 2 Exercise Regimen (Table 3): Replicate 2	Model 3: Flow Rate 1 & 2 Exercise Regimen (Table 3): Replicate 2
Phase II Survey	Phase II Survey	Phase II Survey
Model 8: Flow Rate 1 & 2	Model 2: Flow Rate 1 & 2	Model 4: Flow Rate 1 & 2
Phase II Survey	Phase II Survey	Phase II Survey
NPPTL Post Visit Medical Evaluation ⁵	NPPTL Post Visit Medical Evaluation ⁵	NPPTL Post Visit Medical Evaluation ⁵
Interim Data Analysis		

Visit #7 ⁶ (3 hours)	Visit #8 ⁶ (3 hours)
Pregnancy Test ²	Pregnancy Test ²
NPPTL Pre Visit Medical Evaluation ³	NPPTL Pre Visit Medical Evaluation ³
Model 5: Flow Rate 1 & 2 Exercise Regimen (Table 3): Replicate 2 ¹²	Model 7: Flow Rate 1 & 2 Exercise Regimen (Table 3): Replicate 2 ¹²
Phase II Survey ¹⁰	Phase II Survey ¹⁰
Model 6: Flow Rate 1 & 2 Exercise Regimen (Table 3): Replicate 2 ¹²	Model 8: Flow Rate 1 & 2 Exercise Regimen (Table 3): Replicate 2 ¹²
Phase II Survey ¹⁰	Phase II Survey ¹⁰
NPPTL Post Visit Medical Evaluation ⁵	NPPTL Post Visit Medical Evaluation ⁵
	Data Analysis

1493 Subjects that participated in Phase I must complete consent and screening for Phase II prior to registration if it has been more than a year since their Phase I registration. Rescreening may also be completed within one year, if changes to subject's health and body measurements noted during a study visit (see section 3.1).

² Women of child bearing potential are required to complete a pregnancy test prior to each visit study interventions, which will be reviewed by a U.S. licensed health professional. Only one pregnancy test per 7 calendar days is required and study visits within the same 7 calendar days may waive additional pregnancy tests after first visit in that 7-day period.

³Prior to beginning study interventions at each study visit (for each of 8 total visits), subjects and a U.S. licensed health professional must complete the NPPTL Pre Visit Medical Evaluation form (Appendix L)

4Replicate 1 study interventions should be completed in 4 visits. Each visit, the subject will complete the 30-minute exercise regimen for two PAPR models and two flow rates, for a total of four 30-min tests. They must also complete a Phase II survey (Appendix M) for flow

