rate comparisons and model comfort upon test end for each model. After each 30-minute exercise regimen completed subjects must be given a minimum of a 10-minute break and vitals must be assessed and returned to baseline prior to initiating next exercise regimen, even if for the same model.

⁵Subjects must be given a minimum of a ten-minute break before NPPTL Post Visit Medical Evaluation (Appendix O) completed and a U.S. licensed health professional must review both pre and post test medical evaluations (Appendices L & O) before they are dismissed.

⁶Replicate 2 study interventions should be completed in 4 additional visits. Each visit, the subject will complete the 30-minute exercise regimen for two PAPR models and 2 flow rates, for a total of 4 30-min tests. They must also complete a Phase II survey (Appendix M) for flow rate comparisons and model comfort upon test end for each model. After each 30-minute exercise regimen completed subjects must be given a minimum of a 10-minute break and vitals must be assessed and returned to baseline prior to initiating next exercise regimen, even if for the same model.

3. Phase III Study Calendar

Visit #1 ^{1,4} (3 hours)	Visit #2 ⁴ (3 hours)
Pregnancy Test ²	Pregnancy Test ²
NPPTL Pre Visit Medical Evaluation ³	NPPTL Pre Visit Medical Evaluation ³
Model 1: Exercise Regimen A & B (Table 6) - Replicate 1	Model 5: Exercise Regimen A & B (Table 6) - Replicate 1
Phase III Survey	Phase III Survey
Model 2: Exercise Regimen A & B (Table 6) - Replicate 1	Model 6: Exercise Regimen A & B (Table 6) - Replicate 1
Phase III Survey	Phase III Survey
Model 3: Exercise Regimen A & B (Table 6) - Replicate 1	Model 7: Exercise Regimen A & B (Table 6) - Replicate 1
Phase III Survey	Phase III Survey
Model 4: Exercise Regimen A & B (Table 6) - Replicate 1	Model 8: Exercise Regimen A & B (Table 6) - Replicate 1
Phase III Survey	Phase III Survey
NPPTL Post Visit Medical Evaluation ⁵	NPPTL Post Visit Medical Evaluation ⁵
·	Interim Data Analysis

Visit #3 ^{1,4} (3 hours)	Visit #4 ⁴ (3 hours)
Pregnancy Test ²	Pregnancy Test ²
NPPTL Pre Visit Medical Evaluation ³	NPPTL Pre Visit Medical Evaluation ³
Model 1: Exercise Regimen A & B (Table 6) - Replicate 2	Model 5: Exercise Regimen A & B (Table 6) - Replicate 2
Phase III Survey	Phase III Survey
Model 2: Exercise Regimen A & B (Table 6) - Replicate 2	Model 6: Exercise Regimen A & B (Table 6) - Replicate 2
Phase III Survey	Phase III Survey

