Model 3: Exercise Regimen A & B (Table 6) - Replicate 2	Model 7: Exercise Regimen A & B (Table 6) - Replicate 2
Phase III Survey	Phase III Survey
Model 4: Exercise Regimen A & B (Table 6) - Replicate 2	Model 8: Exercise Regimen A & B (Table 6) - Replicate 2
Phase III Survey	Phase III Survey
NPPTL Post Visit Medical Evaluation ⁵	NPPTL Post Visit Medical Evaluation ⁵

¹Subjects that participated in Phase I must complete consent and screening for Phase II prior to registration if it has been more than a year since their Phase I registration. Rescreening may also be completed within one year, if changes to subject's health and body measurements noted during a study visit (see section 3.1).

² Women of child bearing potential are required to complete a pregnancy test prior to each visit study interventions, which will be reviewed by a U.S. licensed health professional. Only one pregnancy test per 7 calendar days is required and study visits within the same 7 calendar days may waive additional pregnancy tests after first visit in that 7-day period.

³Prior to beginning study interventions at each study visit, subjects and a U.S. licensed health professional must complete the Pre Visit Medical Evaluation form (Appendix L)

⁴Subjects will complete exercise regimens A & B for 4 PAPR models per visit (~3 hours), for a total of four 30-min tests. After the subject completes exercise regimen A, they must receive a minimum of a ten-minute break and vitals must be assessed and have returned to baseline prior to initiating Exercise Regimen B. Subjects must also be provided a minimum of a ten-minute break and vitals must be assessed and have returned to baseline prior to initiating the next models exercise regimen A & B test. Additionally a Phase III Survey (Appendix N) must be completed by the subject at the end of each model tested (four per visit).

⁵Subjects must be given a minimum of a ten-minute break before post visit medical evaluation completed and a U.S. licensed health professional must review their pre and post test medical evaluations (Appendices M & P) before they are dismissed from the visit.

Volunteers Needed in Research Study

Superior Powered Air-purifying Respirator Tests and New Technologies (SPARTAN)

Powered Air-purifying Respirator

study volunteers to participate in research to help improve respirators for use by healthcare workers. This study will be conducted by the National Personal Protective Technology Laboratory (NPPTL) at NIOSH.

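### Appendix A schedules the two Phase II flow rates and the eight PAPR models in one fixed order for every subject and both replicates, so flow rate is aliased with first versus second wearing and model with slot in the cycle

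*Protocol*

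**What the plan says.** **Flow rates.** Section 3.3 numbers the two Phase II rates: "The two PAPR airflow rates tested in Phase II include: 1) 170 L/min for loose-fitting PAPRs and 115 L/min for tight-fitting PAPRs", and second the reduced rates of 125 and 100 L/min. Section 5.3, step 4 reads "During Phase II only, the PAPR flow rate first to be tested will be the fixed manufacture" and stops there. A manufacturer rate is not one of the two rates in section 3.3.

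**Schedule.** The Phase II calendar in Appendix A begins with "Model 1: Flow Rate 1 & 2 Exercise Regimen (Table 3): Replicate 1". It then takes models 2 to 8 in numerical order, two per visit over visits 1 to 4. Visits 5 to 8 begin again with "Model 1: Flow Rate 1 & 2 Exercise Regimen (Table 3): Replicate 2" and keep that order. Section 3.3 agrees: subjects "repeat the same procedure for the second replicate, meaning each subject will complete Phase II" over 8 visits.

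**Model numbers and design class.** Section 3.3 says: "Tight fitting full facepieces (models 1-2) have a tight seal along the chin and sides of face". Models 3 to 6 are loose-fitting hoods and models 7 and 8 loose-fitting facepieces.

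**What is not there.** The protocol mentions no randomisation, counterbalancing or rotation of flow rates or models. The model in section 8.2 names subject, respirator model, work rate or regimen, and flow rate; it has no period, visit or position term. A safety and carry-over reason is given in section 3.2, but only for the light-to-hard order of exercises.

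**The concern.** Each flow comparison is made within a subject on the same device. Under section 5.3, step 8 the subject leaves the chamber and removes the PAPR after each test, so the second flow rate is always tested after a fresh donning. If the same rate is always second, a difference between rates mixes the effect of airflow with whatever changes between first and second wearing: practice, fatigue, or drift of chamber or instruments. These can act in opposite directions. Practice could hide a real loss of protection at reduced flow, and fatigue could create an apparent one.

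The flow contrast serves primary objective a, and section 3.0 says the results will guide decisions on possible changes to 42 CFR 84. The same problem reaches secondary objective b, because design class follows model number and model number follows visit. Test order is set when the data are collected. An analysis plan written later cannot recover a contrast that the schedule has aliased.

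**Working it through.** **1. Layout.** Section 3.3 gives 25 subjects × 8 models × 2 flow rates × 2 replicates = 800 overall SWPF values. This reproduces. It contains 25 × 8 × 2 = 400 pairs of flow tests, all in the same order if the calendar is followed literally.

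**2. Schedule by visit (Appendix A, with the design classes of section 3.3).**

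| Visits (replicate 1, replicate 2) | Models | Design class | Flow order as listed |
|---|---|---|---|
| 1, 5 | 1, 2 | tight-fitting | rate 1, rate 2 |
| 2, 6 | 3, 4 | hood | rate 1, rate 2 |
| 3, 7 | 5, 6 | hood | rate 1, rate 2 |
| 4, 8 | 7, 8 | loose-fitting facepiece | rate 1, rate 2 |

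**3. What can be estimated.** I built the design matrix for this schedule and counted the degrees of freedom left for each effect after adjustment for order.

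- The correlation between flow rate and first/second position is 1.0. Flow has 0 of 1 df after adjustment for position.
- Model has 0 of 7 df after adjustment for slot in the eight-model cycle.
- After adjustment for visit (1 to 8), 4 model df remain. They are the within-visit pairs, and these are aliased with first or second place in the visit.
- With a linear trend over test number 1 to 32 and no separate replicate term, flow keeps its 1 df and model its 7. Standard errors rise by about 0.2% for flow and at most 9% for model contrasts. If a replicate term is fitted as well, flow falls to 0 df.

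Replicate 2 therefore adds precision but does not separate wearing position from flow.

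**4. Effect on the flow test.** The protocol gives no drift, so I assume a range. Take a paired t-test with n = 25 and two-sided α = 0.05 (assumed), no true flow effect, and an order effect of d standard deviations of the paired difference. The order effect enters the flow estimate one for one, so the rejection probability is that of a noncentral t with 24 df and noncentrality d√25 = 5d:

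| d | Noncentrality | Chance of a significant flow effect |
|---|---|---|
| 0 | 0 | 5.0% |
| 0.1 | 0.5 | 7.7% |
| 0.2 | 1.0 | 16.1% |
| 0.3 | 1.5 | 30.2% |
| 0.4 | 2.0 | 48.4% |

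**5. The same idea in SWPF units.** Section 3.1 gives a geometric standard deviation (GSD) of about 1.5 to 3.5. A fall of 0.2 SD on the log scale multiplies SWPF by exp(−0.2 × ln GSD):

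- GSD 1.5: 0.922, a fall of about 8%.
- GSD 2.5: 0.833, about 17%.
- GSD 3.5: 0.778, about 22%.

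This SD is that of a single log SWPF, whereas step 4 uses the SD of a paired difference. The two coincide only when the correlation within a pair is 0.5.

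**6. With counterbalancing.** For a 13/12 split of flow order with position in the model, 20,000 simulated trials per setting gave a bias of about 0 and a rejection rate of about 5% at order effects of 0, 0.2 and 0.4 SD. Power at a paired effect of 0.4 SD is 48.2%, against 48.4% for the fixed order, so protection against order effects costs almost nothing.

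**The case against.** **The order may not be literal.** Step 4 breaks off and names a rate that is not one of the two in section 3.3. The calendar lists rates 1 & 2 without saying one then the other, and section 5.3 speaks neutrally of the PAPR model assigned. A reader might infer from step 4 alone that the reduced rate is always second; it shows only that some rate is fixed as first. The order rests on the calendar read with the numbering in section 3.3. That reading is natural, since nothing calls the calendar illustrative and it uses the model numbers of Table 5, but it remains a reading.

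**Mitigations exist.** An operator assists each donning and verifies the flow. Breaks last at least 10 minutes and vital signs must recover, even between tests of the same model. The tight-fitting models are already worn at screening fit tests. These steps reduce carry-over and learning; they do not make position and flow separable.

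**An analysis could help.** A reader might infer that no analysis removes the problem. That goes too far: a smooth trend over test number can be modelled, on the conditions in the working. It does not cover a first/second-wearing effect or an irregular slot effect. Likewise, each design class is tested at two or more visits, so the aliasing is with slot in the cycle and not with calendar time as such.

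**Two further inferences fail.**

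- Phase III also runs in a fixed order: "After the subject completes exercise regimen A, they must receive a minimum of a ten-minute break" before regimen B. But each regimen in Table 6 has one light, one moderate and one hard exercise, flow is constant, and every model gets both. A-before-B biases neither the flow effect nor the design effect.
- Adding the breaks gives 4 × (30 + 20) + 3 × 10 + 10 + 10 = 250 minutes against a 3-hour visit, which might suggest heavy fatigue. It is not a strict minimum: the in-regimen break is defined by heart-rate recovery, with 10 minutes only approximate. Without those 80 minutes the sum is 170, and the disputed time is rest.

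**Conclusion.** The point holds for Phase II as scheduled. If Appendix A is followed, flow rate is completely aliased with first versus second wearing, and model (with it, design class) with slot in the eight-model cycle. Tight-fitting models always fall at visits 1 and 5, and loose-fitting facepieces at visits 4 and 8. The second replicate repeats the order and does not help.

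The aliasing follows from the schedule; the size of any bias is assumed. For order effects of 0.1 to 0.4 SD of the paired difference, the false-positive rate for flow would be about 8% to 48%. A 0.2 SD downward drift in log SWPF is a fall of about 8% to 22% over the stated GSD range. The documents give neither a drift nor its direction, so nothing here shows that the flow result will be wrong. The plan cannot tell an order effect of this kind from a flow effect, and the remedy is cheap only before testing starts.

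**What to change.** 1. **Complete step 4 of section 5.3** and reconcile it with the two rates in section 3.3. State the intended test order in words in section 5.3 and Appendix A.
2. **Counterbalance flow order within model** across subjects, about 13 in one order and 12 in the other, and reverse each subject's order in replicate 2.
3. **If one order must be fixed in replicate 1**, give the reason and reverse it in replicate 2. The mean of the two replicates then cancels a position effect that is equal in both. The interim analysis after replicate 1 (section 8.2) would stay confounded, and the protocol should say so.
4. **Rotate model order** across subjects with a Latin or Williams square. Because 25 is not a multiple of 8, balance will be approximate.
5. **Include wearing position and visit in the model** alongside flow rate and respirator model.
6. **Keep the light-to-hard exercise order** within a regimen, for which section 3.2 gives its reasons.

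The cost is a prepared order list, revised wording in section 5.3 and Appendix A, and slightly more operator set-up. No visits or subjects are added.
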